10.3.8. Data analysis time

When the subjects in Part I have completed safety and PK assessments in Cycle 1, an analysis will be performed to characterize the PK profile and evaluate the safety and tolerability based on Cycle 1 data. In addition, preliminary myeloprotective efficacy (prevention of chemotherapy-induced myelosuppression) data will be summarized. Data from subjects in Part I may be updated synchronously until the end of the study at the time of data analysis in Part II.

The primary analysis will be performed at the end of Cycle 1 for randomized subjects in Part II. The sponsor 's necessary personnel will be unblinded, but the investigator, subject, and other personnel will remain blinded. The primary measure of myeloprotective efficacy, duration of severe neutropenia (DSN) in Cycle 1, as well as other applicable secondary or exploratory endpoints, will be assessed based on unblinded data.

The second analysis in Part II will be performed after all randomized subjects have completed 6 cycles or end of treatment.

The final analysis of Part II will be performed at the end of the study.

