2.2. Sample Size Determination

The sample size of the second part of this study needs to meet the need to test the efficacy of DSNs in Cycle 1 and is calculated by stochastic simulation. An integrated analysis of the three overseas pivotal studies of Trilaciclib in SCLC showed an approximately 4-day reduction in Cycle 1 DSN in the Trilaciclib group relative to the placebo group. Taking into account the derivation of DSN in Cycle 1, DSN in Cycle 1 is 0 if the subject did not experience any SN during Cycle 1. When there is a large proportion of zero-values, i.e., a large proportion of subjects who do not have any SNs in Cycle 1, the Cycle 1 DSNs more closely follow a Poisson distribution with a mean of -log (proportion of subjects who do not have any SNs in Cycle 1). In the integrated analysis, the proportion of subjects who developed SN during Cycle 1 is 6.7% in the Trilaciclib group compared to 49.6% in the placebo group. Assuming that the proportion of subjects in this study who occurred SN during Cycle 1 is 10% in the Trilaciclib group and 45% in the placebo group, the means of Poisson distributions is 0.105 and 0.598 for the corresponding Trilaciclib and placebo groups, respectively. The stochastic simulation is repeated 10,000 times, each time obtaining the DSN in Cycle 1 from a Poisson distribution and performing comparison between groups by Mann-Whitney-Wilcoxon test, 70 subjects (35 per group) provided approximately 95% power at the test level of $\alpha = 0.05$ (2-sided). Assuming a dropout rate of 12%, the sample size for Part II is 80 subjects (40 per group).

3. Study Conduct

The second part of this study is a randomized double-blind, placebo-controlled study enrolling approximately 80 patients with ES-SCLC, stratified by 1st line vs 2nd/3rd line ES-SCLC, ECOG PS (0-1 vs 2), and presence vs absence of brain metastases, randomized in a 1:1 ratio to Trilaciclib versus placebo where 1st line ES-SCLC patients receive Trilaciclib/placebo in combination with EC regimen (Trilaciclib-EC group and placebo-EC group), 2nd/3rd line ES-SCLC patients will receive Trilaciclib or placebo in combination with Topotecan (Trilacicli-TPT group and placebo-TPT group), and the efficacy of Trilaciclib (prevention of

myelosuppression) will be evaluated with duration of severe neutropenia (DSN) in Cycle 1 as the primary endpoint.

4. Statistical Analysis Methods

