4.4.2.1. Incidence of serious neutropenia events

The total number of SN events is the total number of cycles with at least one ANC value $< 0.5 \times 10^{9}$ /L. For example, two ANC values less than 0.5 x 10⁹/L during Cycle 2 are counted as only one SN event. If a patient does not experience any SN events, the number of SN events for that patient will be counted as zero. Unscheduled data will be included and and actual SN assessment date (non-visit date) will be used. Whether a patient experienced a SN event is a binary variable (yes or no); 'yes' if ≥ 1 cycles with a SN event is observed; and 'no' otherwise.

SN events will be summarized by treatment group using descriptive statistics. Part 2 of the study will analyze the adjusted rate ratio (aRR) between the two treatment groups based on a modified Poisson regression model. The model includes baseline ANC measurement as covariate and IRT-based randomization stratification factors including number of lines of therapy (1st line versus 2nd/3rd line), ECOG (lines 0-1 versus 2) (not included in the actual analysis), and brain metastases (yes versus no), as well as treatment arm as fixed effects. Logarithmic transformed values of the number of cycles will be included in the modeling as offset variables. P-values, aRR (Trilaciclib versus placebo) and their 95% CIs will be provided for the 2-sided tests. In addition, Cochran-Mantel-Haenszel (CMH) weights will be used to calculate the adjusted rate difference between the two arms (Trilaciclib versus placebo) and its 95% CI in Part 2 of the study, and stratified exact CMH method will be used to calculate P values under the 2-sided test according to IRT-based randomization stratification factors to test the stability of the analysis results.

4.4.2.2. Incidence of red blood cell transfusion events occured on/after Week 5

Each red blood cell (RBC) transfusion (including whole blood transfusion and each red blood cell component) occured on/after Week 5 is defined as a separate event and included in the efficacy analysis. Whether a patient experiences a RBC transfusion event is defined as a binary variable (yes or no); "yes" if a total number of RBC transfusion events ≥ 1 is observed, otherwise "no".

The statistical analysis method is similar to that described for SN incidence in Section 4.4.2.1, except hemoglobin (HGB) baseline measurement will be used as covariate instead of

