4.4.2.4. Total occurrence of major adverse hematologic event

Major adverse hematologic event (MAHEs) are composite endpoints to assess the effect of Trilaciclib. MAHE consists of the following 5 component events:

- Involved hospitalization
- Leading to chemotherapy dose reduction
- Febrile neutropenia
- Extended SN (greater than 5 days)
- RBC transfusion occured on/after Week 5.

The total number of events for each MAHE component is the sum of the number of events that occurred on the date of first study drug administration and before the end of the last treatment cycle. The total number of events for MAHEs during treatment is the sum of the number of events for each MAHE component. For patients who does not experience any MAHE, the total number of MAHE events is 0.

MAHEs will be coded using the most current version of MedDRA and the total number of MAHEs, duration of treatment (weeks), weekly event rates, and cumulative event rates every 3 weeks will be summarized by number of lines of treatment. According to the actual MAHEs, the above summaries will be repeated separately by component events , but for MAHE component events leading to chemotherapy dose reduction and SN prolongation, the cumulative

event rates will be summarized by cycle rather than every 3 weeks. Part 2 of the study will also analyze the adjusted rate ratio between the Trilaciclib and placebo groups using a negative binomial regression model. The model includes the three IRT-based randomization stratification factors and treatment group as fixed effects, and the log-transformed values of treatment duration (weeks) or cycle number as offset variables. Two-sided P values, aRR (Trilaciclib versus placebo) and their 95% CIs will be provided. Cumulative incidence of MAHEs within specified subgroups will be presented using forest plots.

Time to first onset (months) for each MAHE component event = (date of first MAHE component event – date of first study drug administration + 1)/30.

For patients who developes MAHEs, the time (months) from the first study drug administration (randomization date in Part II) to the first occurrence of MAHEs will be summarized and Kaplan-Meier curves will be provided. Time to first MAHE refers to the event with the shortest time to first occurrence of the MAHE component; if a patient does not have an MAHE, it will be censored at the end date of the last cycle, date of death, end of study, or last contact date for that patient, whichever cames first.

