4.7. Analysis time

The primary analysis for Part 2 will be performed at the end of Cycle 1 for all randomized subjects. Will be necessary for Sponsor Personnel are unblinded, but the investigator, subject, and other personnel will remain blinded. Assessments will be based on unblinded data Primary endpoint of bone marrow protective efficacy of Trilaciclib and other applicable secondary or exploratory endpoints.

The second analysis in Part 2 will be performed after all randomized subjects have completed 6 cycles or end of treatment.

The final analysis in Part 2 will be performed at the end of the study.

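### The four key secondary endpoints carry unadjusted two-sided p-values and may be tested at more than one analysis, with no testing order, deciding analysis or nominal label

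*SAP*

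**What the plan says.** **Endpoints and tests.** SAP 4.4.2 lists SN, red cell transfusion on or after Week 5, G-CSF use and MAHE.
- SN (4.4.2.1) is analysed by modified Poisson regression: "P-values, aRR (Trilaciclib versus placebo) and their 95% CIs will be provided for the 2-sided tests". A stratified exact CMH p-value is added to check the stability of the result.
- Transfusion (4.4.2.2) and G-CSF use (4.4.2.3) follow the SN method.
- Total MAHE (4.4.2.4) is analysed by negative binomial regression: "Two-sided P values, aRR (Trilaciclib versus placebo) and their 95% CIs will be provided". The same section adds a stratified log-rank p-value for time to first MAHE. Nothing ranks the two. The offset is given as weeks or cycle number, without saying which applies to the total.

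**Timing.** Three Part II analyses are planned. The first is at the end of Cycle 1, with necessary sponsor personnel unblinded. Protocol 10.3.8 says the primary measure, "as well as other applicable secondary or exploratory endpoints, will be assessed based on unblinded data". SAP 4.7 continues: "The second analysis in Part 2 will be performed after all randomized subjects have completed 6 cycles or end of treatment". A final analysis follows at the end of the study. The applicable endpoints are not named, and the contents of the second and final analyses are not listed.

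**Error control.** A significance level appears only in the sample-size text for Cycle 1 DSN. Protocol 10.3.5 describes the key secondary endpoints through descriptive statistics, group differences and 95% confidence intervals, and leaves detailed methods to the SAP.

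**The concern.** The protocol ranks these four endpoints above the other secondaries, and section 7.1 relies on them in particular for the overall protective effect across marrow lineages. The SAP then gives each a between-group p-value. With four endpoints, more than one possible analysis time and no rule for which result counts, a p-value below 0.05 on any one of them has no known error rate.

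Timing matters as well. Sponsor personnel see unblinded results at the end of Cycle 1. An order or deciding analysis chosen after that would be post hoc. At stake is whether the trial can support a claim on any endpoint beyond DSN.

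**Working it through.** **1. The plan's own figure.** SAP 2.2 assumes "SN during Cycle 1 is 10% in the Trilaciclib group and 45% in the placebo group" and states that "the means of Poisson distributions is 0.105 and 0.598 for the corresponding Trilaciclib and placebo groups, respectively".
- Means: −ln(0.90) = 0.105 and −ln(0.55) = 0.598.
- Simulating 35 per group with a two-sided Mann-Whitney-Wilcoxon test at 0.05 (20,000 runs) gives 94.7% power. The plan says "70 subjects (35 per group) provided approximately 95% power at the test level of" 0.05.
- Dropout: 70/0.88 = 79.5, so 80.

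All of this reproduces, and it concerns DSN only.

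**2. One analysis, four endpoints, no true effects.** If the endpoints were independent, the chance of at least one p<0.05 is 1 − 0.95⁴ = 18.5%. Positive correlation lowers it. The documents give no correlations, so a common value ρ is varied in a multivariate normal simulation (400,000 runs).

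**3. SN truly works, the other three do not.** Independent: 1 − 0.95³ = 14.3%. MAHE counts SN lasting over 5 days, so it may respond too. Two nulls then remain: 1 − 0.95² = 9.75% if independent.

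**4. Repeated analyses.** The documents give no accrual time or information fractions. The table assumes information of 0.5 and 1.0 for two analyses, and 0.5, 0.97 and 1.0 for three, with all four endpoints tested each time.

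| ρ | One analysis, four nulls | One analysis, three nulls | Two analyses, four nulls | Three analyses, four nulls |
|---|---|---|---|---|
| 0 | 18.6% | 14.3% | 29.2% | 31.2% |
| 0.3 | 17.4% | 13.7% | 27.6% | 29.2% |
| 0.5 | 15.5% | 12.6% | 24.8% | 26.4% |
| 0.7 | 13.1% | 10.9% | 20.7% | 22.1% |
| 0.9 | 9.4% | 8.3% | 15.1% | 16.2% |

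With information 0.7 and 1.0, two analyses at ρ = 0.9 give 13.8%. So with first-analysis information between 0.5 and 0.7, the range is about 14% to 31%. More information at the first analysis lowers it further: 11.9% at 0.9 and 1.0 with ρ = 0.9.

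**5. Patient-level check.** A null simulation used 10,000 trials of 40 per arm, assumed event rates, 39-week accrual and robust rate-ratio tests. It gives 14.4%, 15.6% and 15.7% at the three analyses taken singly, 20.4% across the first two and 21.1% across all three.

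**6. With a rule.** At one named analysis, a fixed sequence at two-sided 0.05 holds the family error at 5.0%. Bonferroni at 0.05/4 = 0.0125 gives 1 − 0.9875⁴ = 4.9% if the endpoints are independent.

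**The case against.** The strongest reply is that these endpoints are supportive. Protocol 10.3.5 frames them descriptively, and neither document says that p<0.05 on a key secondary will be claimed. A reader might infer that the sponsor intends to claim any of them at 0.05; the text does not say so. This part stands. The percentages are therefore conditional on p<0.05 being read as a claim. It does not remove the gap, because the SAP adds p-values and does not call them nominal. If they are only supportive, one sentence would settle it, at the price of any claim on these endpoints.

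Four further inferences go too far.
- **That no deciding test is named for any endpoint.** For SN, transfusion and G-CSF use, modified Poisson is the analysis and exact CMH the stability check. Only MAHE lacks a ranking, and its two tests address different quantities.
- **That the top of the repeated-analysis range is the expected risk.** It needs uncorrelated endpoints. MAHE contains transfusion and prolonged SN, and G-CSF use follows neutropenia. Treating four endpoints at three analyses as 12 independent tests (46%) would be wrong. Retesting at the final analysis is also an assumption. These events occur during chemotherapy and are nearly complete by the second analysis, so a third adds only about 1 to 2 points.
- **That most patients have incomplete treatment at the first analysis.** It falls about 3 weeks after the last entry. Under uniform accrual over A weeks, the share at least 18 weeks (six cycles) past entry is (A − 15)/A. That exceeds half once A passes 30, and is 24/39 = 62% at 39 weeks. The documents give no accrual time.
- **That the DSN test is compromised.** It has one primary strategy and one primary analysis time.

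**Conclusion.** The concern holds as a gap in pre-specification. The four key secondary endpoints have unadjusted two-sided p-values, possibly at more than one analysis, with no order, deciding analysis or nominal label, and MAHE has two unranked tests.

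If p<0.05 is read as a claim, the risk of at least one false positive is about 9% to 18.5% at one analysis (ρ from 0.9 to 0), or 8% to 14% if SN truly works and the other three do not. Over repeated analyses it is about 14% to 31%, under the assumed correlations and information. Every scenario tried with at least two true nulls exceeds 5%, but no single value can be derived from the documents. The change is cheap and affects what the trial can conclude, so it should be made.

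**What to change.** Before the first unblinding, amend SAP 4.4.2 and 4.7:
- Make the second analysis, with all patients through 6 cycles or end of treatment, the only inferential analysis of the key secondary endpoints.
- If DSN is significant, test the four in a prespecified fixed sequence at two-sided 0.05, stopping claims at the first non-significant result. The sponsor chooses and justifies the order; one example is SN, G-CSF use, MAHE, transfusion. In the integrated analysis in Protocol Table 3 the placebo-versus-trilaciclib differences are 52.9% − 11.4% = 41.5 points for SN, 56.3% − 28.5% = 27.8 for G-CSF use and 26.1% − 14.6% = 11.5 for transfusion. MAHE is not in that table, so its place needs its own rationale.
- Use the modified Poisson test for SN, G-CSF use and transfusion, and one named test for MAHE with its offset stated.
- Label all other p-values nominal: the first and final analyses of these endpoints, CMH, the MAHE test not chosen, and the nine endpoints in 4.4.3.3 that borrow the SN method although 4.4.3 calls for descriptive summaries.

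The cost is SAP wording, with no loss on the DSN test. The downside is that endpoints after the first non-significant one cannot be claimed.

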1.3.3. Efficacy data

Trilaciclib efficacy refers to the prevention of chemotherapy induced bone marrow suppression. A summary of myeloprotective endpoint measures for the three clinical trials conducted in SCLC patients is presented in Table 3. The trial results showed that Trilaciclib had a significant effect in preventing bone marrow suppression, supporting the conduct of a Phase 3 clinical study based on this data in China to evaluate the safety and efficacy of Trilaciclib in Chinese patients.

	Study	G1T28-02	Part II	Stu	dy G1T28	8-05	Study	G1T28-03	Part II	Inte	grated Ana	lysis
Endpoint	Plac + E/C (N = 38)	Trila + E/C (N = 39)	P value	Plac + E/C/A (N = 53)	Trila + E/C/A (N = 54)	P value	Plac + TPT 1.5 mg/m ² (N = 29)	Trila + TPT 1.5 mg/m ² (N = 32)	P value	Placebo + Chemothe rapy (N = 119)	Trilaciclib + Chemothe rapy (N = 123)	
Cycle 1 DSN, mean (SD)	3 (3.9)	0 (0.5)	< 0.0001	4 (4.7)	0 (1.0)	< 0.0001	7 (6.2)	2 (3.9)	< 0.0001	4 (5.1)	0 (1.8)	< 0.0001
Occurrence of severe neutropenia, N (%)	16 (42.1)	2 (5.1)	0.0049	26 (49.1)	1 (1.9)	< 0.0001	22 (75.9)	13 (40.6)	0.016	63 (52.9)	14 (11.4)	< 0.0001
G-CSF use rate, N (%)	24 (63.2)	4 (10.3)	0.0003	25 (47.2)	16 (29.6)	0.0686	19 (65.5)	16 (50.0)	0.2544	67 (56.3)	35 (28.5)	< 0.0001
Occurrence of febrile neutropenia TEAEs, N (%)	3 (7.9)	1 (2.6)	0.4544	3 (5.7)	1 (1.9)	NE	5 (17.2)	2 (6.3)	NE	11 (9.2)	4 (3.3)	0.0889
Occurrence of RBC transfusion in Cycle 5 and beyond, N (%)	9 (23.7)	2 (5.1)	0.0338	11 (20.8)	7 (13.0)	0.1335	12 (41.4)	10 (31.3)	0.3222	31 (26.1)	18 (14.6)	0.0252
Number of Red Blood Cell Transfusion Events on/after Week 5 (Weekly Occurrence)	0.019	0.005	0.0208	0.026	0.017	0.1954	0.063	0.026	0.0302	0.031	0.015	0.0027
Erythropoiesis StimulatingAgent Use, N (%)	2 (5.3)	1 (2.6)	NE	6 (11.3)	3 (5.6)	0.3343	6 (20.7)	1 (3.1)	0.0673	14 (11.8)	4 (3.3)	0.0254
Number of Erythropoiesis Stimulating Agents Used (Events Per Week)	0.021	0.016	0.4368	0.06	0.026	0.2412	0.143	0.059	0.1228	0.064	0.016	0.0359
Occurrence of Grade 3/4 Decreased Hemoglobin Levels, N (%)	7 (18.4)	4 (10.3)	0.1682	15 (28.3)	10 (18.5)	0.2369	17 (58.6)	12 (37.5)	0.093	38 (31.9)	25 (20.3)	0.0279
Occurrence of platelet transfusion, N (%)	0	2 (5.1)	NE	2 (3.8)	1 (1.9)	NE	9 (31.0)	8 (25.0)	0.3222	11 (9.2)	10 (8.1)	0.9564

Table 3 Summary of Trilaciclib Bone Marrow Protection Endpoint Data from Three Clinical Trials in SCLC

Version No.: V1.4, March 21, 2022

	Study	G1T28-02	Part II	Stu	dy G1T28	-05	Study	G1T28-03	Part II	Integ	grated Ana	lysis

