4.4.3. Other Secondary Efficacy Endpoints

Descriptive statistics will be used to summarize the following additional secondary efficacy endpoints. Descriptive statistics for continuous data will include means, medians, standard deviations and ranges, and categorical data will provide frequencies and percentages.

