4.4.3.3. Other dichotomous endpoints

The total number of events below is the total number of cycles with at least one event. If a patient does not experience any of the following events during the treatment period, the number of events for that patient is zero. 'Yes' if ≥ 1 of the following events are observed; otherwise 'No'.

- Incidence of Grade 3 and 4 Hematologic Toxicities: Grade 3 and 4 hematologic toxicities refers to hematology laboratory results with CTCAE Grade 3 or 4.
- Incidence of platelet transfusion (during chemotherapy)
- Incidence of febrile neutropenia

Each of the following events with a unique start date will be defined as a separate event during the treatment period. Yes if the total number of the following events observed is ≥ 1 , otherwise no.

- Incidence of intravenous or oral antibiotics
- Incidence of infectious serious adverse events
- Incidence of serious adverse events of lung infection

Determine if the following medications is used in that cycle by comparing the start and end dates of each use of the following medications with the start and end dates of the treatment cycle. The total number of events with the following medications is the total number of cycles with at least one dose of the following medication. If a patient did not take the following medications during the treatment period, the number of events for that patient is 0.

- Erythropoiesis-stimulating agent (ESA) Usage
- Recombinant human interleukin-11 (IL-11) use rate
- Thrombopoietin (TPO) use

The total number of events as well as the incidence of the above dichotomous variables will be summarized descriptively and tabulated in detail by patient. The statistical analysis approach is similar to that described for SN incidence in Section 4.4.2.1, except that baseline ANC measurements will not be included as covariates in the modified Poisson regression model.

In addition, for comparing the incidence of antibiotic administration, SAEs of infection, and SAEs of lung infection between the Trialciclib and placebo groups, the offset variable in the modified Poisson regression model will be the log transformed duration of treatment (weeks) rather than the number of cycles.

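### For rare yes/no endpoints, the modified Poisson p-value and confidence interval break down when one arm has no events, and the SAP has no rule for that case

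*SAP*

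**What the plan says.** For severe neutropenia (SN) incidence, SAP 4.4.2.1 states: "Part 2 of the study will analyze the adjusted rate ratio (aRR) between the two treatment groups based on a modified Poisson regression model". It adjusts for baseline ANC and randomization factors, and "Logarithmic transformed values of the number of cycles will be included in the modeling as offset variables". On output, "P-values, aRR (Trilaciclib versus placebo) and their 95% CIs will be provided for the 2-sided tests".

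The same paragraph adds a CMH-weighted rate difference with a 95% CI, and a second p-value: "stratified exact CMH method will be used to calculate P values under the 2-sided test according to IRT-based randomization stratification factors". That second p-value is there to check the stability of the results.

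Sections 4.4.2.2 (RBC transfusion) and 4.4.2.3 (G-CSF use) refer back to this method. Section 4.4.3.3 does so for nine further endpoints: "The statistical analysis approach is similar to that described for SN incidence in Section 4.4.2.1", but without baseline ANC. They include febrile neutropenia, platelet transfusion, infection SAEs, lung-infection SAEs and use of ESA, IL-11 or TPO. The parent section 4.4.3 introduces the other secondary endpoints differently: "Descriptive statistics will be used to summarize the following additional secondary efficacy endpoints".

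The SAP allows small strata to be merged for the DSN analyses (4.4.1.1 and 4.4.1.2). It has no provision for an arm with no events.

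**The concern.** A log-link model has no finite estimate of the rate ratio when one arm has no events. The fitted log ratio runs toward minus infinity and the software stops at an arbitrary large value, near -20. A model-based variance would become very large at that point. The sandwich variance does not, because the empty arm's residuals are essentially zero. Dividing a huge coefficient by an ordinary standard error gives an extreme Wald statistic. The p-value then reports little more than that one arm was empty.

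With 40 per arm, an empty arm is a realistic outcome for several 4.4.3.3 endpoints. The output table could show p<0.0001 from a single event beside an exact p-value of 1.0, with no prespecified statement of which one to read. Protocol 7.1 uses the secondary endpoints to judge protection across bone marrow cell lines, so these rows will be read, whichever arm happens to be empty.

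**Working it through.** **The plan's own figure.** The documents state no type I error for these endpoints, so only the design that fixes the arm size can be reproduced. The Poisson means are -log(0.90) = 0.105 and -log(0.55) = 0.598. Simulating 10,000 trials with 35 per group and the Mann-Whitney test gives 94.4% to 94.5% power (stated: about 95%). Then 70/(1 - 0.12) = 79.5, or 80 patients, 40 per arm. Both reproduce.

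**Inputs.** n = 40 per arm (SAP 2.2). Two-sided 0.05 is assumed, because the SAP allocates no alpha here. Event rates come from Protocol 1.3.3, Table 3.

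**Mechanism, unadjusted.** The sandwich variance of the log ratio is the sum of two terms:
- Empty arm: sum(mu²)/(sum mu)² = 1/40 = 0.025.
- Arm with k events: (1 - k/40)/k.

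For 0/40 versus 1/40, SE = sqrt(0.025 + 0.975) = 1.0. The fitted coefficient is about -20.4, so p is about 2e-92. Fisher's exact p is 1.0.

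For 0/40 versus 2/40, SE = sqrt(0.025 + 0.475) = 0.707 and z is about -29. Fisher's exact p is 0.49.

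By contrast, 1/40 versus 3/40 gives p = 0.33. The empty arm is what breaks the test.

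**Frequency with no effect.** With q = (1 - p)^40, the probability that exactly one arm is empty is 2q(1 - q). The total rejection rate comes from enumerating two Binomial(40, p) arms and counting a single empty arm as a rejection. Fisher's test stands in for the stratified exact CMH.

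| True rate, both arms | One arm empty | Robust Wald rejects | Fisher rejects |
|---|---|---|---|
| 1% | 44.29% | 44.29% | 0.00% |
| 1.72% (peak) | 50.00% | 50.00% | 0.01% |
| 2% | 49.41% | 49.41% | 0.01% |
| 3% | 41.65% | 41.65% | 0.07% |
| 5% | 22.40% | 22.45% | 0.40% |
| 8% | 6.87% | 7.35% | 1.17% |
| 9.2% | 4.12% | 4.94% | 1.48% |
| 10% | 2.91% | 3.98% | 1.68% |

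At rates up to 5%, trials with events in both arms add at most 0.05 percentage points.

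**Adjusted model.** 800 trials per rate were simulated with treatment, line, brain metastases, baseline ANC and a log-cycles offset, under assumed covariate and cycle distributions. Rejection was 44%, 47%, 42% and 22% at rates of 1%, 2%, 3% and 5% with a binary response, and 44%, 48%, 43% and 22% with a count response. Among datasets with one empty arm, 92% to 98% gave p<0.0001 at rates of 1% to 5%, and all did at 8% to 10%. The remainder had p-values up to 0.98, so the breakdown is near-universal but not automatic.

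**Where this trial may sit.**
- Lower first-line placebo rates in Table 3: platelet transfusion 3.8%, ESA use 5.3%, febrile neutropenia 5.7%. Null rejection is 33%, 20% and 17%.
- The other first-line trial had placebo rates of 0% for platelet transfusion, 11.3% for ESA use and 7.9% for febrile neutropenia. At the last two, rejection is 3.1% and 7.6%.
- Integrated placebo rates: febrile neutropenia 9.2%, platelet transfusion 9.2%, serious infection 10.1%, ESA use 11.8%. Rejection is 3% to 5%, so there is no inflation.

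**The case against.** Several points on the other side stand.

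- **The test statistic is inferred.** The SAP says modified Poisson, not Wald. A score test would reject in 1.4% to 5.9% of null trials at rates of 2.6% to 10%.
- **The pooled population may not be in the affected range.** Part II mixes first-line and topotecan patients. Topotecan placebo rates in Table 3 are 17.2% for febrile neutropenia, 20.7% for ESA use and 31.0% for platelet transfusion, and the integrated rates show no null inflation.
- **Nothing is formally declared.** The endpoints are introduced as descriptive, no alpha or success rule is attached, and the exact CMH p-value is already planned for the same comparison.

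A reader might infer more than the documents support:

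- **That the key secondary endpoints are compromised.** Integrated placebo rates are 26.1% for RBC transfusion, 52.9% for SN and 56.3% for G-CSF use. Under no effect at 26.1%, exactly one empty arm occurs about once in 90,000 trials, and more rarely at higher rates. Few RBC transfusions at the end-of-Cycle-1 analysis is speculative, since SAP 4.7 limits that analysis to applicable endpoints.
- **That the chance of one empty arm at the integrated two-arm rates is a false-positive rate.** It is 27% for febrile neutropenia (9.2% versus 3.3%) and 26% for ESA use (11.8% versus 3.3%). Both assume a real effect, and 25.6 of 27.1 points and 26.0 of 26.4 points are an empty trilaciclib arm, the true direction.
- **That NE in Table 3 shows an earlier sparse-data rule.** The row "Occurrence of platelet transfusion, N" does show NE for 0 versus 2 events. But febrile neutropenia 3 versus 1 is NE in one trial and p = 0.4544 in another, and intravenous antibiotics 8 versus 7 is also NE. The documents do not explain the entry.

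**Conclusion.** The concern holds for the rare endpoints of SAP 4.4.3.3. With 40 per arm and no effect, the model p-value is spuriously below 0.05 in about 22% to 50% of trials at true rates of about 1% to 5%. The excess is small at 8% and gone by 9% to 10%. SN, G-CSF use and RBC transfusion are practically unaffected once follow-up is complete.

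This rests on the robust-variance Wald reading, a common event rate in both arms and an assumed 0.05 threshold. The consequence is a misleading p-value and interval in the report. It is not a formal false claim, because no decision depends on these p-values. It is still worth correcting: the plan as written would print those figures, and the choice between two conflicting p-values should not be made after unblinding.

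**What to change.** Add to SAP 4.4.2.1, and apply by reference in 4.4.2.2, 4.4.2.3 and 4.4.3.3:

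> If either arm has no patients with the event, the aRR and its CI are shown as not estimable, the modified Poisson p-value is not reported, and the reported two-sided p-value is the planned stratified exact CMH p-value, with the rate difference and an exact CI.

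Naming the test statistic for the modified Poisson model in the same place would remove the ambiguity.

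The trigger should be zero events, not a wider threshold such as fewer than five. The excess comes almost entirely from empty arms. At the assumed 10% Cycle 1 SN rate on trilaciclib, four or fewer events in 40 has probability 63%, so a wider trigger would often displace the model p-value for SN, where it works.

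The cost is one sentence. The exact CMH and the rate difference are already planned, but the method for the exact interval has to be named. The exact test is conservative with sparse data, so those p-values will be larger: 5 versus 0 events gives 0.055 and 6 versus 0 gives 0.026 by Fisher's test.
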